1.0 DEVICE DESCRIPTION

The Hydrus Microstent is a crescent-shaped implantable microstent pre-loaded onto a hand-held delivery system.

The microstent (Figure 1) is composed of nitinol, a metal alloy of nickel (Ni) and titanium (Ti). Nitinol has been used extensively in a variety of implantable devices for its proven properties of flexibility, strength and biocompatibility. As a shape memory alloy, nitinol has super elastic properties making it suitable as a support structure in Schlemm's canal. Its flexibility and small size allows delivery of the microstent through tortuous, restrictive passages with minimal force. The implant is laser cut from nitinol tubing to a proprietary design with alternating "spines" for structural support and "windows" to provide outflow pathways for aqueous humor. After laser cutting, the shape of the implant is heat-set to a curvature that matches the curvature of Schlemm's canal and is electro-polished to create a smooth biocompatible surface. The microstent is approximately 8mm in overall length with major and minor axes of 292µm and 185µm, respectively. The length and curvature of the implant are designed to occupy approximately 90° or 3 clock hours of Schlemm's canal. The implant is designed to have adequate structural thickness to support the tissue of the canal while providing maximum open flow areas through the canal, with the proximal portion of the implant exiting the canal through the trabecular meshwork to allow inflow of aqueous humor from the anterior chamber.

[figure not shown]

FIGURE 1: HYDRUS IMPLANT

The microstent is implanted into the eye using a hand-held delivery system (**Figure 2**) that provides for manual delivery of the implant through a stainless steel cannula into the target site in the eye. The delivery system was designed for usability to provide smooth tracking and controlled delivery of the microstent into Schlemm's canal. The delivery system is an ergonomic design for use in either the right or left hand, allowing for surgeon individual preference and hand position. To accommodate a wide range of hand positions, a rotatable sleeve at the distal end allows positioning and alignment of the cannula by the surgeon to direct the implant into Schlemm's canal. The tracking wheel on the delivery system serves as the control mechanism to advance the implant into the canal or retract the implant into the cannula.

[figure not shown]

FIGURE 2: HYDRUS DELIVERY SYSTEM

To deliver the microstent into Schlemm's canal, the cannula of the delivery system is inserted through a clear corneal incision (approximately 1.5mm in length). The cannula tip is then advanced through the trabecular meshwork until it enters Schlemm's canal and the entry point into the meshwork is coincident with the end of the cannula bevel. The target tissue is visualized using a gonioscopic prism. After observing that the distal cannula tip is properly positioned through the trabecular meshwork into Schlemm's canal, the tracking wheel on the delivery system is used to advance and release the microstent.

The Hydrus Microstent is packaged in sterile-barrier packaging and provided "STERILE" by gamma irradiation.

2.0 ALTERNATIVE PRACTICES AND PROCEDURES

There are several alternatives for the correction of mild to moderate POAG. These alternatives include:

- Non-surgical treatment, such as IOP-lowering medications (topical eye drops or systemic IOP lowering drugs)
- Laser treatment
- Other incisional glaucoma surgery

Each alternative has its own advantages and disadvantages. A patient should fully discuss these alternatives with his/her physician to select the method that best meets expectations and lifestyle.

3.0 MARKETING HISTORY

The Hydrus Microstent is currently approved for commercial distribution in the European Union, Canada, Australia, New Zealand, Costa Rica and Columbia.

The Hydrus Microstent has not been withdrawn from marketing for any reason relating to the safety and effectiveness of the device.

4.0 SUMMARY OF NONCLINICAL STUDIES

A. BIOCOMPATIBILITY TESTING

Biocompatibility testing was performed on the Hydrus implant or representative samples of the finished device (**Table 1A**) and on the patient-contacting components of the Hydrus delivery system (**Table 1B**). The biocompatibility testing was performed in accordance with *ISO 10993-1 - Biological evaluation of medical devices - Part 1: Evaluation and testing within a risk management process and relevant related sub-standards, including:*

- Part 3: Tests for genotoxicity, carcinogenicity and reproductive toxicity
- Part 5: Tests for in vitro cytotoxicity
- Part 6: Tests for local effects after implantation
- Part 10: Tests for irritation and skin sensitization
- Part 11: Tests for systemic toxicity

All biocompatibility testing was conducted in accordance with the provisions of 21 CFR 58, Good Laboratory Practice for Nonclinical Laboratory Studies.

TABLE 1A: BIOCOMPATIBILITY TESTING OF THE HYDRUS IMPLANT

Test	Test Method	Results		
Cytotoxicity	MEM Elution ISO 10993-5	Non-cytotoxic		
Cytotoxicity	Agarose Overlay (Direct Contact) ISO 10993-5	Non-cytotoxic		
Cytotoxicity	Cell Growth Inhibition Assay ISO 10993-5	Negative		
Sensitization	Guinea Pig Maximization ISO 10993-10	Non-sensitizer		
Intracutaneous Reactivity	Rabbit Intracutaneous Reactivity ISO 10993-10	Non-irritant		
Acute Systemic Toxicity	Mouse USP Systemic Injection ISO 10993-11	Non-toxic		
Material Mediated Pyrogenicity	Rabbit Pyrogen ISO 10993-11:2006	Non-pyrogenic		
Subacute Intraperitoneal Toxicity	Mouse 14-Day Intraperitoneal Injection ISO 10993-11	Non-toxic		
Subchronic Intravenous Toxicity	Mouse 14-Day Intravenous Injection ISO 10993-11	Non-toxic		
Mutagenicity	Ames Reverse Mutation ISO10993-3	Non-mutagenic		
Mutagenicity	Mouse Micronucleus ISO10993-3:2003	Non-genotoxic		
Mutagenicity	Mouse Lymphoma ISO10993-3:2003	Non-mutagenic		
Intramuscular	Rabbit Muscle Implantation (13 weeks)	No different than		
Implantation	ISO 10993-6:2007	control		
Chronic Toxicity	6-Month Ocular Implantation Testing in Rabbits	No different than control		

TABLE 1B: BIOCOMPATIBILITY TESTING OF THE HYDRUS DELIVERY SYSTEM

Test	Test Method	Results		
Cytotoxicity	MEM Elution ISO 10993-5	Non-cytotoxic		
Sensitization	Guinea Pig Maximization ISO 10993-10	Non-sensitizer		
Intraocular Irritation	Intraocular Exposure in Rabbits	Non-irritant		
Intracutaneous Irritation	Rabbit Intracutaneous Reactivity ISO 10993-10	Non-irritant		
Acute Systemic Toxicity	Mouse USP Systemic Injection ISO 10993-11	Non-toxic		
Material Mediated Pyrogenicity	Rabbit Pyrogen ISO 10993-11	Non-pyrogenic		

B. PHYSICOCHEMICAL TESTING

Physicochemical testing was conducted to physically characterize and verify the stability of the microstent throughout the potential implant life span. Physicochemical testing (**Table 2**) was conducted on the Hydrus implant (or representative samples of the finished device) in accordance with *ANSI Z80.27 - Ophthalmics - Implantable Glaucoma Devices* and *FDA Guidance Document - Premarket Studies of Implantable Minimally Invasive Glaucoma Surgical (MIGS) Devices (December 15, 2015).*

TABLE 2: PHYSICOCHEMICAL TESTING OF THE HYDRUS IMPLANT

Test	Purpose	Results			
Corrosion Resistance	Determine susceptibility of microstent to galvanic corrosion per ASTM F 2129-08	Microstent is considered corrosion resistant			
Exhaustive Extraction	Determine identity and amount of extractable substances	No extractable substances at levels that would affect the human eye			
Leachables	Determine identity and amount of saline leachables	No leachable substances at levels that would affect the human eye			
Nickel Elution	Quantify amount of nickel ion released from microstent	Risk of adverse effects resulting from nickel leaching is negligible			
Hydrolytic Stability	Demonstrate 5 year accelerated hydrolytic stability of the microstent in situ	Microstent is hydrolytically stable for 5 years; no detectable adverse effect on surface characteristics of finished microstents			
Insoluble Organics	Evaluate microstent for evidence of inorganic compounds on the finished device at the end of the manufacturing process	No significant levels of insoluble organics detected			

C. PHYSICAL AND MECHANICAL TESTING

The Hydrus implant and delivery system were subjected to physical and mechanical testing in accordance with ANSI Z80.27 (**Table 3**).

TABLE 3: PHYSICAL AND MECHANICAL TESTING OF THE HYDRUS MICROSTENT

Test	Purpose	Results			
Material Properties Nitinol (NiTi) Alloy	Verify nitinol base material satisfies composition and mechanical characteristics for surgical implants per ASTM F2063-12	Each lot of microstents is provided with a Certificate of Conformance to ASTM F2063-12			
Austinetic Finish Transition Temperature (A _f)	Verify A _f transition temperature of microstent following heat-set operation satisfies specification of 16±3° C	Each lot of microstents is tested for A _f transition temperature by differential scanning calorimetry testing per ASTM F2004			
Dimensions	Verify overall dimensions are within specifications	Each lot of microstents is inspected for nominal length, wall thickness and radius of curvature			
Edge and Surface Quality	Verify edges and surface of microstent are smooth, free of cracks, protrusion, pits, dings, inclusions and stringers	Each lot of microstents is subjected to surface/edge inspection by light microscopy and SEM			
Structural Integrity	Verify microstent satisfies mechanical strength requirements per ANSI Z80.27-14	Tensile force testing shows force at breakage > 0.5 N, satisfying requirements of ANSI Z80.27-2014			
Outflow Facility	Verify microstent is able to increase outflow of aqueous humor sufficient to lower IOP in bench test model	Benchtop testing demonstrates significant increase in outflow facility in cadaver eyes			
Magnetic Resonance Imaging Compatibility	Evaluate the compatibility of the microstent with current standard magnetic resonance imaging techniques	Microstent shown to be "MR-conditional" and labeled appropriately per ASTM F2503-13			
Delivery System Performance	Verify delivery system consistently satisfies performance requirements for microstent delivery	Performance testing demonstrates that the microstent is consistently delivered under conditions of in vitro bench testing and simulated in vivo use in cornea rim tissue			

D. STERILIZATION, PACKAGE INTEGRITY, SHELF LIFE, AND TRANSPORT STABILITY

The Hydrus Microstent is supplied with the implant pre-loaded in the handheld delivery system. The device is sealed in sterile-barrier (Tyvek®) packaging and packaged in a chipboard shelf box.

The packaged device is sterilized by exposure to gamma radiation. Microbiological studies have been conducted to demonstrate that the packaged device satisfies domestic and international requirements to be labeled 'STERILE' with a Sterility Assurance Level (SAL) of 10^{-6} . The sterilization cycle was validated in accordance with the provisions of *ISO* 11137-1:2006 - Sterilization of health care products – Radiation – Part 1: Requirements for development, validation and routine control of a sterilization process for medical devices and *ISO* 11137-2:2012 - Sterilization of health care products – Radiation - Part 2: Establishing the sterilization dose. The methodology used was that applicable to substantiating 25 kGy as a minimum sterilization dose (Method VD_{max}25). Successful completion of the sterilization validation qualifies dose monitoring as a means for routine lot release of the device.

Sterilization, packaging, shipping, and shelf life studies were conducted to verify that the packaging for the device maintains a sterile barrier and that the device performance meets product specifications through the labeled shelf life. The results of the sterilization, packaging, shelf life and transport stability studies are summarized in **Table 4**.

TABLE 4: STERILIZATION, PACKAGING, TRANSPORTATION AND SHELF LIFE TESTING

Test	Purpose	Results				
Gamma Irradiation Sterilization Validation	Demonstrate device is 'STERILE' to an SAL of 10 ⁻⁶	Satisfies requirements of ISO 11137-1 to be labeled 'Sterile' with an Sal of 10 ⁻⁶				
Bioburden	Establish upper limit for product bioburden to establish sterility of (< 200 CFU/Device)	Bioburden testing shows results ≤ 200 CFU/Device				
Bacterial Endotoxin	Verify bacterial endotoxin levels satisfy FDA Guidance for single-use ophthalmic devices (< 0.2 EU/Device)	Bacterial endotoxin testing shows results < 0.2 EU/Device				
Package Evaluation – Bubble Leak	Verify package seal integrity	No bubble leak per ASTM F2096				
Package Evaluation – Seal Peel Test	Verify package seal integrity	Package seal peel strength ≥ 1.0 Lb _f				
Transport Stability	Verify package and device stability after transportation challenges	Packaging and device satisfy specifications after transport challenges per ASTM D4169, distribution cycle 13				
Shelf Life Stability	Verify sterile-barrier packaging and device satisfy specifications through labeled expiration date	Sterile-barrier packaging and device satisfy specifications after aging to the labeled expiration date				

5.0 STUDY METHODS

A. SELECTION OF PATIENTS

Only subjects who meet the inclusion and exclusion criteria will be eligible for enrollment in this study.

B. GLAUCOMA DIAGNOSIS

Glaucoma is a progressive optic neuropathy that results in characteristic optic disc and visual field changes. To qualify for the study, all subjects must have optic disc changes characteristic of glaucoma.

C. INCLUSION CRITERIA

Subjects must meet the following inclusion criteria to be eligible for the study eye:

- Male and female patients, at least 45 years of age
- An operable age-related cataract with BCVA of 20/40 or worse, eligible for phacoemulsification; if BCVA is better than 20/40, testing with a BAT meter on a medium setting must result in BCVA 20/40 or worse
- A diagnosis of POAG treated with 1 to 4 hypotensive medications
- Optic nerve appearance characteristic of glaucoma
- Medicated IOP ≤ 31 mmHg
- Diurnal IOP ≥ 22 mmHg and ≤ 34 mmHg after wash out of ocular hypotensive medications
- IOP increase > 3 mmHg after wash out of ocular hypotensive medications
- Visual field examination using Humphrey 24-2 SITA standard, meeting protocol specified minimum criteria for glaucoma defined as:
 - 1. **Mild:** visual field loss on Humphrey visual field testing, with mean deviation (MD) between 0 and -6dB; fewer than 25% of points depressed below the 5% level and fewer than 15% of points depressed below the 1% level on pattern deviation plot; and no point within central 5° with sensitivity <15dB.
 - 2. Moderate: visual field loss on Humphrey visual field testing, with mean deviation worse than -6dB but no worse than -12dB; fewer than 50% of points depressed below the 5% level, and fewer than 25% of points depressed below the 1% level on pattern deviation plot; no points within central 5° with sensitivity of ≤0dB; and only one hemifield containing a point with sensitivity <15dB within 5° of fixation.

- In subjects where the VF exam is not confirmatory for glaucomatous defect, retinal nerve fiber layer optical scanning laser imaging supporting ophthalmoscopy findings shall be performed
- Shaffer grade ≥ III in all four quadrants
- Cup:disc (c:d) ratio ≤ 0.8
- Absence of peripheral anterior synechiae (PAS), rubeosis or other angle abnormalities that could impair placement of the implant
- Subject is able and willing to attend scheduled follow-up exams for 2 years post-operatively (and up to 5 years postoperatively as part of a post-approval study)
- Subject understands and signs the informed consent

D. Intraoperative Eligibility Criteria

Individuals who meet the following intraoperative eligibility criteria in the study eye will be randomized into the treatment or control arms of this study.

Subjects must have:

- An intact and centered capsulorrhexis
- An intact posterior capsular bag
- A well-centered monofocal IOL placed in the capsular bag
- A clear view of an open angle and visualization of the angle with direct gonioscopy following intracameral instillation of a miotic agent

Subjects must not have:

- Evidence of zonular dehiscence/rupture
- Intraoperative floppy iris syndrome

E. EXCLUSION CRITERIA

Excluded from the study will be individuals with the following characteristics. Unless specified otherwise, all ocular criteria refer to the study eye only.

- Closed angle forms of glaucoma
- Congenital or developmental glaucoma
- Secondary glaucoma (such as neovascular, uveitic, pseudoexfoliative, pigmentary, lens-induced, steroid-induced, trauma induced, or glaucoma associated with increased episcleral venous pressure).
- Use of more than 4 ocular hypotensive medications (combination medications count as two medications).
- Previous argon laser trabeculoplasty, trabeculectomy, tube shunts, or any other prior filtration or cilioablative surgery.

- Prior surgery for an ab-interno or ab-externo device implanted in or through the Schlemm's Canal.
- Inability to complete a reliable 24-2 SITA Standard Humphrey visual field on the study eye at screening (fixation losses, false positive errors and false negative errors should not be greater than 33%).
- Use of oral hypotensive medication for glaucoma for treatment of the fellow eye.
- Subjects with advanced glaucoma or any subject who presents with an unacceptable risk to the subject of a washout of ocular hypotensive medications.
- Best corrected visual acuity worse than 20/80 in the fellow eye.
- A 24-2 SITA Standard Humphrey visual field mean deviation (MD) of worse than -12dB in the fellow eye.
- Central corneal thickness > 620 microns and < 480 microns.
- Proliferative diabetic retinopathy.
- Previous surgery for retinal detachment.
- Previous corneal surgery or clinically significant corneal dystrophy, e.g.,
 Fuch's dystrophy (>12 confluent guttae)
- Unclear ocular media preventing visualization of the fundus or anterior chamber angle.
- Degenerative visual disorders such as wet age-related macular degeneration.
- Clinically significant ocular pathology, other than cataract and glaucoma.
- Clinically significant ocular inflammation or infection within 6 months prior to screening.
- Presence of extensive iris processes that obscure visualization of the trabecular meshwork.
- Unable to discontinue use of blood thinners in accordance with surgeon's standard postoperative instructions.
- Known or suspected elevated episcleral venous pressure due to Sturge Weber, nanophthalmos, orbital congestive disease.
- Uncontrolled systemic disease that in the opinion of the Investigator would put the subject's health at risk and/or prevent the subject from completing all study visits.
- Current participation or participation in another investigational drug or device clinical trial (which includes the fellow eye) within the past 30 calendar days.
- Pregnant or nursing women; or women of child bearing age not using medically acceptable contraceptives.

F. CONSENT

Participation in the study is voluntary. When it has been established that the subject is eligible for possible enrollment into the study, written informed consent (ICF) will be obtained.

G. ENROLLMENT

Patients who sign the informed consent form (ICF) are considered enrolled. Only after ICF is obtained should study specific exams and wash out be initiated.

H. WASH OUT

After the subject has successfully completed the preoperative screening exam, the subject will be instructed to discontinue ocular hypotensive medications in the designated treatment eye for the appropriate washout period.

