6.0 CLINICAL FOLLOW-UP SCHEDULE

All subjects will be scheduled to return for follow-up examinations at defined intervals through 24 months. **Table 5** shows the schedule of events and procedures at each protocol-required visit.

TABLE 5: SCHEDULE OF EVENTS AND PROCEDURES

Procedure	Screening (Both Eyes) (w/in 30d of washout start)	Baseline (w/in 13d of minimum washout)	Surgery (w/in 14d of minimum washout)	1D Postop	7D Postop (±2d)	1M Postop (±7d)	3M Postop (±14d)	6M Postop (±21d)	12M Postop (-28d/ +42d)	18M Postop (±28d)	24M Postop (-28d/ +42d)	3Y, 4Y & 5Y Postop (±84d)
Ophthalmic and medical history	Х											
Ocular Medication Status	Х	Х	Х	Х	Х	Х	Х	Х	Х	Х	Х	X ⁵
Glaucoma Medication Status	Х	Х	Х	Х	Х	Х	Х	Х	Х	Х	Х	Χ5
Manifest Refraction	Х	Х			Х	Х	Х	Х	Х	Х	Х	
BCVA	X (Snellen)	X (ETDRS)		X (pinhol e) (Snellen	X (ETDRS)	X (ETDRS)	X (ETDRS)	X (ETDRS)	X (ETDRS)	X (ETDRS)	X (ETDRS)	X (Snellen)
IOP (Goldmann Applanation Tonometry)	Х			х	Х	Х	Х	Х	X ²	Х	χ2	X ₆
Washed Out Diurnal IOP (Goldmann Applanation Tonometry)		X1							X1		X1	
Pachymetry CCT	х							Х	Х		Х	Х
Gonioscopy	Х				Х	Х	Х	Х	Х	Х	Х	Х
Slit Lamp Exam	Х	Х		Х	Х	Х	Х	Х	Х	Х	Х	Х
Visual Field (Humphrey 24-2 SITA-Std)	Х							Х	Х		Х	Х
Fundus Exam/Disc evaluation	х					Х		Х	Х		Х	Х
Specular Microscopy	Х						Х	X ⁷	Χ7	X ⁷	χ7	Х7
Nerve Fiber Layer Imaging	χ³											
Ocular Symptom Questionnaire		Х							Х		Х	
Adverse Event Assessment		Χ4	Х	Х	Х	Х	Х	Х	Х	Х	Х	Χ8

^{*}Washed out diurnal IOP measurements will be performed after subject has washed out of any ocular hypotensive medications. All diurnal IOP measurement must be done PRIOR to the Gonioscopy, Fundus Exam and contact Pachymetry. An additional visit may be necessary to perform the diurnal IOP measurements.

*Only required for those subjects taking ocular hypotensive medications at the time of this visit.

*Only required for those subjects whose VF testing was not confirmatory for glaucomatous defect per the protocol defined criteria.

*Only adverse events associated with the ocular medication wash out.

*Study eye only for ocular medications other than hypotensive medications.

*Single operator tonometry may be conducted at 3, 4 and 5 year visits.

*Includes specular microscopy of the fellow eye for the central region only

*Report all SAEs and only study eye ocular AEs.

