7.0 STATISTICAL ANALYSIS PLAN - STUDY ENDPOINTS

A. THE PRIMARY EFFECTIVENESS ENDPOINT FOR THIS STUDY

Percentage of subjects with a reduction of at least 20% (i.e., \geq 20%) in mean diurnal IOP from baseline in the study eye at 24 months following medication washout. These subjects were defined as "IOP responders."

Subjects were defined as non-responders if they did not achieve the primary effectiveness endpoint, they were missing 24-month IOP assessment outcomes, if ocular hypotensive medications were not washed out at the 24-month visit, if they underwent an IOP-affecting secondary surgical procedure (i.e., iridotomy, iridectomy, trabeculectomy, glaucoma shunt implantation, argon laser trabeculoplasty, selective laser trabeculoplasty), or other surgery that would affect IOP.

B. THE SECONDARY EFFECTIVENESS ENDPOINT FOR THE STUDY

The mean diurnal unmedicated IOP change from baseline at 24 months was compared between the Hydrus group and control group.

Each endpoint requires a comparison between the Hydrus and control groups. The primary effectiveness analysis will be performed using the Intent to Treat (ITT) population, consisting of all randomized subjects grouped according to their randomization assignment.

With regard to safety, anticipated and unanticipated AEs will be reported for all subjects randomized in the study. Best corrected visual acuity (BCVA), central corneal pachymetry, slit lamp and fundus exams, gonioscopy and central corneal endothelial cell density (ECD) will also be used to assess safety.

C. ACCOUNTABILITY OF PMA COHORT

Subjects will be analyzed according to 3 separate population cohorts:

ITT Population – all subjects randomized and grouped according to their randomization assignment (as randomized). The ITT will be used for the analyses of the primary and secondary effectiveness endpoints.

Per Protocol Population – ITT subjects that met the following conditions:

- Met all protocol eligibility criteria
- Had treatment consistent with randomization schedule
- Completed the 24-month medication washout without secondary surgical intervention to control IOP or additional procedures that could affect IOP (such as cyclodialysis cleft)

- Had preoperative visual field mean deviation (MD) of <0
- Without major protocol deviation established before the data review and database closure

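### The central corneal thickness exclusion joins two ranges with *and*, so read literally it excludes no eye; the connective needs correcting before eligibility, deviations and Per Protocol membership are judged on it

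*Combined protocol and SAP*

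**What the plan says.** Section 5.0 E opens with "Excluded from the study will be individuals with the following characteristics" and adds "Unless specified otherwise, all ocular criteria refer to the study eye only". One of the listed characteristics is "Central corneal thickness > 620 microns and < 480 microns". The criterion appears once. It is not restated elsewhere as an eligible range or with a different connective, and no reason is given for the two limits.

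Three other places bear on it:

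- The schedule in section 6.0 (Table 5) has a row "Pachymetry CCT" that is marked at screening, so the value is available when eligibility is decided.
- Section 7.0 C defines the Per Protocol population by several conditions, the first of which is "Met all protocol eligibility criteria".
- Section 7.0 B names the measures that will be used to assess safety: "Best corrected visual acuity (BCVA), central corneal pachymetry, slit lamp and fundus exams, gonioscopy" and endothelial cell density. This is the only analytic use of pachymetry that the plan states.

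Sections 7.0 B and 7.0 C assign the effectiveness endpoints to the intent-to-treat population, meaning everyone randomized, grouped as randomized.

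**The concern.** An exclusion criterion removes a subject who has the listed characteristic. Here the characteristic is a conjunction of two ranges that do not overlap, so no one can have it. An *and* between limits is correct when it describes a range to be admitted, as in the inclusion criterion "Diurnal IOP ≥ 22 mmHg and ≤ 34 mmHg after wash out of ocular hypotensive medications". Carried over to a list of what is to be excluded, with the inequalities pointing outward, it empties the rule.

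At stake is the classification of any eye outside 480 to 620 microns that reaches randomization. On the literal text such an eye breaks no criterion and satisfies the eligibility condition for Per Protocol. On the evident intent it is an eligibility violation and leaves that set. The plan does not say which reading governs. If a site had also screened on the literal text, the randomized population itself would include such eyes.

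**Working it through.** The plan gives no figure of its own to reproduce here. The check has a logical part, which needs no assumption, and an illustrative part, which does.

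**Logical part.** Let C be the central corneal thickness of the study eye in microns. The two limits cannot refer to different eyes, because the list is restricted to the study eye.

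- As written: exclude if C > 620 and C < 480. Since 480 < 620, no value meets both. Of the 601 whole-micron values from 300 to 900, 0 satisfy the rule.
- With *or*: exclude if C > 620 or C < 480. On the same grid, values up to 479 and from 621 are excluded, and 480 to 620 inclusive remain eligible.

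Two example eyes under each reading:

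| C (microns) | Literal *and* | Intended *or* |
|---|---|---|
| 460 | eligible; meets the Per Protocol eligibility condition | ineligible; outside Per Protocol if randomized |
| 640 | eligible; meets the Per Protocol eligibility condition | ineligible; outside Per Protocol if randomized |

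**Illustrative part.** The documents give no distribution for corneal thickness. Assume it is normal with mean m and standard deviation s, with m from 535 to 555 and s from 30 to 40 microns. The share of screened eyes covered by the intended rule is

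P(C < 480) + P(C > 620) = Φ((480 − m)/s) + 1 − Φ((620 − m)/s).

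For m = 545 and s = 35, the standardized limits are (480 − 545)/35 = −1.857 and (620 − 545)/35 = 2.143. The tails are 3.16% and 1.61%, which sum to about 4.8%.

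| Assumed mean | SD 30 | SD 35 | SD 40 |
|---|---|---|---|
| 535 | 3.6% | 6.6% | 10.1% |
| 545 | 2.1% | 4.8% | 8.2% |
| 555 | 2.1% | 4.8% | 8.2% |

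The rows for 545 and 555 agree because both means lie 5 microns from 550, the midpoint of 480 and 620. Widening the assumed means to 530 to 560 raises the top of the range to about 12% (mean 530, SD 40). Under every one of these assumptions the literal rule covers 0%.

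**The case against.** The strongest reply is that no one would read the line literally. Under a heading that lists excluded characteristics, it is naturally taken as naming two excluded ranges, and no other reading gives it any function. The document is loose with *and* elsewhere: in the same list, the visual field reliability criterion joins three error rates with *and* although a failure on any one is plainly meant to count. If sites apply the evident meaning, no out-of-range eye is randomized and the two readings give the same Per Protocol set. This largely stands. The documents do not show how the rule was applied, and misapplication should not be presumed. It does not rescue the sentence, because a listing programmed from the text would return no violations whatever sites did.

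Per Protocol also requires the absence of a major protocol deviation. That condition could remove an out-of-range eye by judgment, but section 7.0 C does not define what is major, so it does not settle the reading.

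A reader might go further and infer that a safeguard on tonometry has failed, since "Washed Out Diurnal IOP (Goldmann Applanation Tonometry)" supplies both the entry limits and the endpoint. The documents do not support that. They state no purpose for the thickness limits, and the only analytic role given to pachymetry is safety. Nor is this criterion the only one that bears on the cornea: the same list excludes previous corneal surgery and clinically significant dystrophy.

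A reader might also infer bias in the primary result. None is shown. The effectiveness endpoints are analysed by intent to treat. Thickness is measured at screening and randomization follows during surgery, so the wording cannot act differently by arm through eligibility. The primary endpoint is a percentage change from baseline within the eye.

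**Conclusion.** The line is wrong as written. That the literal rule excludes no eye is certain and rests on no assumption. The practical consequence is conditional: it arises only if an eye outside 480 to 620 microns is randomized, or if eligibility and deviations are checked against the literal text. The clearest exposure is deviation classification and Per Protocol membership, not the primary or secondary effectiveness analysis.

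The figure of about 2% to 10% (about 5% at mean 545, SD 35) rests wholly on the assumed normal distribution. It is the share of screened eyes to which the intended rule would apply. It is not the share misclassified in this trial, nor an effect on any result. The severity is minor.

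**What to change.** The sponsor should confirm that both ranges were meant to be excluded, then replace *and* with *or* in section 5.0 E, leaving 620 and 480 microns as they stand. The plan should state that eligibility checks, deviation classification and the eligibility condition for Per Protocol all use the corrected wording. If any out-of-range eyes have been randomized, they should be listed and classified on that wording before the database is closed.

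The cost is one word in the protocol and a check that the eligibility form and the analysis programs agree with it. Those are not among the documents, so whether they repeat the slip is unknown. Sample size, endpoints and the intent-to-treat analysis are unaffected.
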